#### 4.1.4.1 Rules for down-titration in case of intolerance to BI 685509

If a patient has an AE that, based on Investigator judgement, may be related to trial medication, the down-titration rules below must be followed. These rules apply if the patient has successfully completed the dose titration period (i.e. Visit 4) and is either still taking their final assigned dose of trial medication, or if they have missed  $\leq 3$  consecutive doses. If the patient has not successfully completed the dose titration period (i.e. Visit 4), down-titration is not permitted; in case of persistent AEs or severe effects, the patient must permanently discontinue treatment (refer to [Section 3.3.4.1](#)).

- if the patient is receiving [REDACTED] BID BI 685509 the dose will be down-titrated one level to [REDACTED] BID BI 685509

Once down-titration has taken place, no further up-titration will be permitted.

If a patient continues to have an AE, or a new AE develops, that based on Investigator judgement, may be related to trial medication, a second down-titration will be permitted:

- if the patient is receiving [REDACTED] BID BI 685509 the dose will be down-titrated to [REDACTED] BID BI 685509

Down-titration must not be performed by taking less than the two daily doses or by splitting tablets so that a whole tablet is not taken. Down-titration will be managed through the IRT system (refer to [Section 4.1.4](#)). After the successful completion of the dose titration period (i.e. Visit 4), in case of persistent AEs despite down-titration, or severe effects at any dose, permanent treatment discontinuation should be considered (refer to [Section 3.3.4.1](#)). Patients who are down-titrated will need to return to the investigational site to receive their continuing supply of trial medication, either at the next scheduled visit or via an unscheduled visit.

 One dose refers to an individual time point e.g. morning dose or evening dose.

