### 3.3.4.1 Discontinuation of trial treatment

Ideally, the patient should attend all remaining visits. Should the patient not agree, at least phone contacts should occur at the scheduled visit time points, should that not be acceptable, a phone contact once a year or at the end of the planned observation period should occur to collect the most relevant information: vital status (please see [section 5.2.6.2.1](#) ), outcome events, adverse events, or last contact date in case of lost to follow-up.

An individual patient will discontinue trial treatment (BI 685509 and empagliflozin) if:

- the patient wants to discontinue trial treatment. The patient will be asked to explain the reasons but has the right to refuse to answer.
- the patient has repeatedly shown to be non-compliant with important trial procedures and, in the opinion of both the investigator and sponsor representative, the safety of the patient cannot be guaranteed as he / she is not willing or able to adhere to the trial requirements in the future.
- the patient needs to take concomitant medication that interferes with the safety/efficacy of the investigational medicinal product or other trial treatment (refer to [Section 4.2.2.1](#)). If short-term, acute use of a restricted concomitant therapy is required (e.g. 5-7 days of antibiotic treatment for an infection), this will not automatically require discontinuation of BI 685509 or empagliflozin. Similarly, if a patient needs to modify a dose, where only a stable dose is permitted (e.g. NSBBs / carvedilol, statins, anti-viral therapy for HBV, pioglitazone, GLP1-agonists, or vitamin E), this also will not automatically require discontinuation. In both cases, the Sponsor should be consulted.
- the patient experiences a severe infection, e.g. with SARS-CoV-2, as determined by the Investigator
- the patient meets the criteria for hepatic injury (refer to [Section 5.2.6.1.4](#) and [Appendix 10.2](#))
- the patient has an acute liver decompensation event such as VH, new-onset of ascites, new-onset of overt encephalopathy, or other new-onset decompensation event based on Investigator judgement
- patients with worsening of their liver function (e.g. from Child-Turcotte-Pugh A to Child-Turcotte-Pugh B with clinical evidence of deteriorating liver function in the opinion of the Investigator). Refer to Child-Turcotte-Pugh classification method in [Appendix 10.3](#)

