In case of a temporary discontinuation, trial medication (BI 685509 and/or empagliflozin) should be restarted if medically justified; refer to [Section 4.1.4](#) for details, including instructions regarding dose adjustments.

If new efficacy / safety information becomes available, Boehringer Ingelheim will review the benefit-risk-assessment and, if needed, pause or discontinue the trial treatment for all patients or take any other appropriate actions to guarantee the safety of the trial patients.

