#### 4.1.4 Drug assignment and administration of doses for each patient

Trial medication will be dispensed at the investigational sites in accordance with the [Flow Chart](#). At dispensing visits patients will be given the appropriate number of medication kits for BI 685509 (range 1-2) and empagliflozin (range 1-2) depending on the interval between the visits (for further kit details refer to [Section 4.1.6](#)). The last dose of BI 685509 will be administered in the evening of the day before the EoT visit and the last dose of empagliflozin in the morning of the day before the EoT visit.

All patients will start on a dose of [REDACTED] BI 685509 *BID* at Visit 2. Treatment group 4 will receive a fixed dose of 10mg empagliflozin *QD* in addition. 7 days later, at Visit 3, and again at Visit 4, 7 days after Visit 3, all patients will be up-titrated to a dose of [REDACTED] BI 685509 *BID*, and then to the maintenance dose of [REDACTED] BI 685509 *BID*.

Patients will be informed of the dose titration period and will be made aware that up-titration for BI 685509 is being used. If a patient does not tolerate an up-titration, e.g. due to orthostatic dysregulation, the rules in [Section 4.1.4.1](#) must be followed. From Visit 4 onwards, patients of the treatment group 1, 2, 3 and 4 will continue to receive the maximum dose of [REDACTED] BI 685509 (plus 10mg empagliflozin *QD* for group 4 only) until reaching the EoT visit (8 weeks after starting the trial medication).

If a patient has an AE that, based on Investigator judgement, may be related to BI 685509 or empagliflozin, the trial medication can either be:

- interrupted (i.e. the trial medication is stopped, and subsequently re-started. The up-titration approach described above is followed.)

OR

- the dose can be reduced (down-titrated) for BI 685509 if the patient has successfully completed the dose titration period (i.e. Visit 4). No dose reduction is allowed for empagliflozin.

For further details refer to Sections [4.1.4.1](#) and [4.1.4.2](#).

All trial medication assignments, including up / down-titrations for BI 685509 and provision of replacement kits, will be managed through the IRT system. Down-titrations of BI 685509 must not be performed by instructing the patient to take less than the two daily doses (refer to [Section 4.1.4.1](#)).

Table 4.1.4: 1 Drug assignment and dosage by treatment group

Randomisation Allocation	Week 1 of Treatment	Week 2 of Treatment	Week 3 of Treatment Onwards

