Patients who fail to follow these instructions should have the visit re-scheduled as soon as possible, ideally on the following day (refer to [Section 6.1](#)). On days with no scheduled visit the patient will self-administer their medication at home. Patients should be instructed to bring all unused trial medication and empty wallets / packaging with them when they return for clinic visits to the investigational site.

In case of a temporary interruption to treatment, refer to Sections [3.3.4.1](#), [4.1.4.1](#) and [4.1.4.2](#).

In the event of force majeure or other disrupting circumstances (e.g. pandemic, war; refer to [Section 6](#)) physical patient visits to sites may not be feasible or may need to be restricted to ensure patient safety. Based on a thorough assessment of the benefits and risks, the Investigator may still decide to continue trial medication, and, if acceptable according to local law and regulations, trial medication may be shipped from the site to the patient's home.

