#### **4.1.4.2 Rules for re-starting up-titration in case of interruption of BI 685509**

An interruption of BI 685509 may have an influence on the tolerability. Hence, if a patient has missed  $> 3$  consecutive doses of trial medication for any reason (e.g. due to an AE, or for compliance reasons), the rules below will apply for the safety of the patient. If  $\leq 3$  consecutive doses of trial medication have been missed and there is no related AE, then the next dose of trial medication should be taken as scheduled.

- after an interruption of trial medication of  $> 3$  consecutive doses, the patient should re-start the dose titration period at [REDACTED] *BID* BI 685509
- before any further up-titration occurs the patient must have taken the preceding dose for at least 7 consecutive days. This applies throughout the treatment period
  - this may mean that a patient due to be up-titrated at Visit 3 or 4 (as per [Table 4.1.4: 1](#)) is held at their current dose until their next scheduled visit. They could also be up-titrated at an unscheduled visit once this requirement is met
- if interruption occurs after Visit 4, subsequent up-titration will be allowed either at a scheduled visit or at an unscheduled visit

Patients with an interruption of trial medication will need to return to the investigational site to receive their continuing supply of trial medication, either at the next scheduled visit or via an unscheduled visit.

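### For a patient who is down-titrated and later misses more than 3 consecutive doses, Protocol 4.1.4.1 forbids up-titration while 4.1.4.2 allows it, with no ceiling or precedence stated

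*Protocol*

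**What the plan says.** **The ban.** Protocol 4.1.4.1 governs dose reduction for intolerance after the titration period has been completed at Visit 4. Its opening limits the rules to a patient who "is either still taking their final assigned dose of trial medication, or if they have missed" no more than 3 consecutive doses. Two successive reductions are possible. After the first comes the sentence: "Once down-titration has taken place, no further up-titration will be permitted". It carries no end point and no exception.

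**The re-start.** Protocol 4.1.4.2 applies once more than 3 consecutive doses have been missed for any cause, and names adverse events and poor compliance as examples. Then "the patient should re-start the dose titration period at" a dose that is redacted. Each level must be taken for at least 7 consecutive days before the next. The last bullet reads: "if interruption occurs after Visit 4, subsequent up-titration will be allowed either at a scheduled visit or at an unscheduled visit".

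**The parent section.** Protocol 4.1.4 lists interruption as one way to handle a possibly related adverse event: "interrupted (i.e. the trial medication is stopped, and subsequently re-started. The up-titration approach described above is followed". The approach it points to ends at the maintenance dose.

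**Cross-references.** Section 4.1.4 also says "In case of a temporary interruption to treatment, refer to Sections" 3.3.4.1, 4.1.4.1 and 4.1.4.2, so it names both rules. Section 3.3.4.1 says that after a temporary stop "trial medication (BI 685509 and/or empagliflozin) should be restarted if medically justified", and refers back to 4.1.4 for dose adjustments.

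**The concern.** A patient who is reduced for intolerance and later has a gap of more than 3 doses falls under both rules. The first step back, to the re-start dose, breaches neither. The conflict begins with the next upward step, which 4.1.4.1 forbids and 4.1.4.2 allows.

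What is at stake is re-exposure to a dose already reduced for a possibly drug-related event. Section 3.2 calls orthostatic dysregulation dose-limiting, section 1.2.1 reports a dose-dependent QTcF increase of up to 13.7 ms in patients with cirrhosis, and 4.1.4.2 itself notes that an interruption may affect tolerability. Two sites could read the text differently and dose similar patients differently.

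**Working it through.** The plan gives no figure on this point, so there is none to reproduce. The check has two parts.

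**1. The rules side by side**

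| Question | 4.1.4.1 | 4.1.4.2 | 4.1.4, interruption bullet |
|---|---|---|---|
| Who is covered? | Anyone already down-titrated | Anyone with more than 3 missed doses | Anyone interrupted for a possibly related event |
| Up-titration? | Not permitted | Allowed, also after Visit 4 | Follow the titration scheme |
| Highest dose? | Current reduced dose | Not stated | Maintenance dose, by reference |
| Previously down-titrated patients mentioned? | Yes | No | No |
| Precedence stated? | No | No | No |

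Sections 3.1, 3.3.4.1 and 4.2.2.1 add no ceiling or order of precedence. The redactions hide dose values; the readable sentences around them contain no cap.

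**2. Can it happen within 8 weeks?**

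Inputs from the Flow Chart, 4.1.4 and 4.1.4.2: Visit 4 on Day 15; end of treatment (EoT) on Day 57 ± 5; last BI 685509 dose on the evening before EoT; at least 7 days per level. Assumptions: the redacted re-start dose is the starting dose, there are three levels as in Table 4.1.4:1, and a second down-titration returns the patient to the starting level.

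Let R be the re-start day and L the last dosing day (EoT − 1). The middle dose is possible from R + 7 and maintenance from R + 14.

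- At least 7 days at maintenance: R + 20 ≤ L.
- At least 1 day at maintenance: R + 14 ≤ L.
- At least 7 days at the middle dose (relevant after two down-titrations): R + 13 ≤ L.

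| EoT day | L | Latest R, 7 days at maintenance | Latest R, 1 day at maintenance | Latest R, 7 days at middle dose |
|---|---|---|---|---|
| 52 | 51 | 31 | 37 | 38 |
| 57 | 56 | 36 | 42 | 43 |
| 62 | 61 | 41 | 47 | 48 |

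Earliest R: maintenance from Day 15, down-titration on Day 16, four missed twice-daily doses on Days 17–18, so R = 19. The middle dose is then possible from Day 26 and maintenance from Day 33. With EoT on Day 57, the re-start window for a 7-day return to maintenance is Days 19–36, or 36 − 19 + 1 = 18 days.

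Return to maintenance needs four separate dispensing events after Visit 4: the reduction, the re-start, the middle dose and maintenance. Only Visits 5 and 6 are scheduled before EoT, so at least 4 − 2 = 2 are unscheduled visits. Both sections allow these.

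**The case against.** The strongest reply is that the text already protects the patient.

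- **The ban is specific and has no expiry.** The post-Visit-4 bullet in 4.1.4.2 can be read as saying where up-titration may take place, without cancelling an earlier intolerance restriction. Re-starting and then holding at the re-start dose complies with both sections. This stands, and it makes continuation of the ban the better reading.
- **The entry condition does not switch the ban off.** One could argue that 4.1.4.1 stops applying after more than 3 missed doses. But its opening describes when a reduction may be made, whereas the ban follows once one has been made. Section 4.1.4 also sends sites to 4.1.4.1 during an interruption. This stands too. If the argument were accepted, it would lead back to the reduced dose with no ceiling.
- **The bullets in 4.1.4 are alternatives.** They offer interruption or reduction and do not address one followed by the other. That makes 4.1.4 weaker evidence than 4.1.4.2.
- **There are safeguards.** Section 3.1 makes each upward step conditional on tolerance. Re-start must be medically justified, vital signs and ECGs are repeated after dosing during up-titration, blood pressure is measured daily at home, and the investigator may discontinue treatment. These lower the risk, but none states a ceiling. For short-term restricted therapy and changes to stable-dose medication, 3.3.4.1 adds "In both cases, the Sponsor should be consulted". That does not reach the adverse-event and compliance interruptions that 4.1.4.2 names.
- **IRT manages all titration steps.** It may already cap the dose. Its specification is not in the documents, so this can be neither relied on nor excluded.

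A reader might infer that the protocol directs sites to re-escalate patients to a dose they did not tolerate, or that sites cannot satisfy both sections. The documents support neither, for the reasons in the first two bullets.

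**Conclusion.** The inconsistency is real and narrow. 4.1.4.1 forbids what 4.1.4.2 literally permits for the same patient, and nothing states a ceiling or an order of precedence. The likely intent is that the ban continues, but the text leaves a site to infer it.

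It needs a down-titration followed by a gap of more than 3 doses, early enough to climb again. The documents give no rate for either event, so the number affected cannot be calculated; few patients, possibly none, is a judgement. The 18-day window assumes the earliest possible sequence and the unredacted dose levels set out above.

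It would be wrong to infer that the trial's result is at risk. Sample size is untouched. The primary analysis handles the listed intercurrent events by treatment policy, and SAP 7.4.4 already repeats it without patients who had a down-titration or interruption. This is a low-frequency safety point, worth correcting because the correction is so small.

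**What to change.** Add to 4.1.4.2: *The restriction in 4.1.4.1 continues to apply after an interruption. A previously down-titrated patient re-starts at the re-start dose and must not be titrated above the reduced dose reached before the interruption.*

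The sponsor must also settle one choice, because a cap at the reduced dose implies a step up that the ban, as worded, forbids:

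- **Allow the step back up to the reduced dose.** Amend the ban in 4.1.4.1 to except re-titration under 4.1.4.2 up to that dose.
- **Keep the ban absolute.** State in 4.1.4.2 that the patient stays at the re-start dose.

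Either choice prevents return to the dose that was not tolerated. For a twice-down-titrated patient the two coincide, if the re-start dose is the starting dose. Add a cross-reference in the interruption bullet of 4.1.4 and confirm that IRT enforces the rule.

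The cost is a clause, a cross-reference, possibly one exception in 4.1.4.1, and an IRT check, with no change to visits, sample size or analysis. The downside is that a few patients whose interruption had nothing to do with tolerability stay below the maintenance dose.

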#### **4.1.4.2 Rules for re-starting up-titration in case of interruption of BI 685509**

An interruption of BI 685509 may have an influence on the tolerability. Hence, if a patient has missed  $> 3$  consecutive doses of trial medication for any reason (e.g. due to an AE, or for compliance reasons), the rules below will apply for the safety of the patient. If  $\leq 3$  consecutive doses of trial medication have been missed and there is no related AE, then the next dose of trial medication should be taken as scheduled.

- after an interruption of trial medication of  $> 3$  consecutive doses, the patient should re-start the dose titration period at [REDACTED] *BID* BI 685509
- before any further up-titration occurs the patient must have taken the preceding dose for at least 7 consecutive days. This applies throughout the treatment period
  - this may mean that a patient due to be up-titrated at Visit 3 or 4 (as per [Table 4.1.4: 1](#)) is held at their current dose until their next scheduled visit. They could also be up-titrated at an unscheduled visit once this requirement is met
- if interruption occurs after Visit 4, subsequent up-titration will be allowed either at a scheduled visit or at an unscheduled visit

Patients with an interruption of trial medication will need to return to the investigational site to receive their continuing supply of trial medication, either at the next scheduled visit or via an unscheduled visit.

#### **4.1.5 Blinding and procedures for unblinding**

Although a randomization is applied to NASH patients with T2DM, the patients, investigators and sponsors will stay unblinded due to the open-label nature of this trial.

#### **4.1.6 Packaging, labelling, and re-supply**

The investigational medicinal products will be provided by BI or a designated Clinical Research Organisation (CRO). They will be packaged and labelled in accordance with the principles of Good Manufacturing Practice. Re-supply to the sites will be managed via an IRT system, which will also monitor expiry dates of supplies available at the sites.

In this trial, each medication kit with *BID* BI 685509 will contain one wallet and each wallet will hold 20 film-coated tablets (i.e. seven days treatment plus three days reserve). Each medication kit with *QD* empagliflozin will contain one wallet and each wallet will hold 14 film-coated tablets (i.e. seven days treatment plus seven days reserve). The number of kits dispensed at each dispensing visit, will be sufficient to cover both the planned number of weeks of treatment between visits, and the use of any permitted visit windows.

For details of packaging and the description of the label, refer to the ISF.

---

 One dose refers to an individual time point e.g. morning dose or evening dose.

#### **4.1.7 Storage conditions**

Drug supplies will be kept in their original packaging and in a secure limited access storage area according to the recommended storage conditions on the medication label. A temperature log must be maintained for documentation.

If the storage conditions are found to be outside the specified range, the Clinical Research Associate (CRA), as provided in the list of contacts in the ISF, must be contacted immediately.

#### **4.1.8 Drug accountability**

The Investigator or designee will receive the trial medication delivered by the Sponsor or delegate when the following requirements are fulfilled:

- approval of the CTP by the Institutional Review Board (IRB) / Independent Ethics Committee (IEC)
- availability of a signed and dated clinical trial contract between the Sponsor or delegate and the investigational site
- approval / notification of the regulatory authority, e.g. competent authority (CA)
- availability of the curriculum vitae of the Principal Investigator
- availability of a signed and dated CTP
- availability of the proof of a medical license for the Principal Investigator (if applicable)
- availability of FDA Form 1572 (if applicable)

Trial medication is not allowed to be used outside the context of this CTP. It must not be forwarded to other Investigators or clinics. Patients should be instructed to return unused trial medication.

The Investigator or designee must maintain records of the medication's delivery to the trial site, the inventory at the site, the use by each patient, and the return to the Sponsor or warehouse / drug distribution centre or alternative disposal of unused medication. If applicable, the Sponsor or warehouse / drug distribution centre will maintain records of the disposal.

These records will include dates, quantities, batch / serial numbers, expiry ('use-by') dates, and the unique code numbers assigned to the trial medication and trial patients. The Investigator or designee will maintain records that document adequately that the patients were provided the doses specified by the CTP and reconcile all trial medication received from the Sponsor. At the time of return to the Sponsor and / or appointed CRO, the Investigator or designee must verify that all unused or partially used trial medication has been returned by the clinical trial patient and that no remaining supplies are in the Investigator's possession.

